4.2.5. Patient Reported Outcomes

4.2.5.1. Respiratory Infection Symptom Questionnaire (RSV-PRO)

4.2.5.1.1. Definition

The RSV Patient-Reported Outcome (RSV-PRO) measure is a 32-item patient-reported questionnaire used to assess the severity of RSV symptoms over the past 24 hours and is exactly the same questionnaire as the FLU-PRO questionnaire.

The presence and severity of RSV signs and symptoms are assessed across 6 body systems affected by RSV: Nose (4 items), Throat (3 items), Eyes (3 items), Chest/Respiratory (7 items), Gastrointestinal (4 items), and Body/Systemic (11 items) with 5 possible levels (not at all (level code = 0), a little bit (level code = 1), somewhat (level code=2), quite a bit (level code=3), very much (level code = 4).

The RSV-PRO domain scores are defined as indicated in [Table 2](#). These will be calculated at each time point a questionnaire was filled. A change from baseline will also be calculated.

Table 2. RSV-PRO domain scores

Domain	Items	Scoring	Minimum Data Requirement
Nose	Runny or dripping nose Congested or stuffy nose Sneezing Sinus pressure	Arithmetic mean of 4 items within Nose domain	Daily score for 3 of 4 items must be present to calculate domain score
Throat	Scratchy or itchy throat Sore or painful throat Difficulty swallowing	Arithmetic mean of 3 items within Throat domain	Daily score for 2 of 3 items must be present to calculate domain score
Eyes	Teary or watery eyes Sore or painful eyes Eyes sensitive to light	Arithmetic mean of 3 items within Eyes domain	Daily score for 2 of 3 items must be present to calculate domain score
Chest/Respiratory	Trouble breathing Chest congestion Chest tightness Dry or hacking cough Wet or loose cough Coughing Coughed up mucus or phlegm	Arithmetic mean of 7 items within Chest/Respiratory domain	Daily score for 5 of 7 items must be present to calculate domain score
Gastrointestinal	Felt nauseous Stomach ache How many times did you vomit? How many times did you have diarrhea?	Arithmetic mean of 4 items within Gastrointestinal domain	Daily score for 3 of 4 items must be present to calculate domain score
Body/Systemic	Headache	Arithmetic mean of	Daily score for 8 of 11

	Head congestion Felt dizzy Lack of appetite Sleeping more than usual Body aches or pains Weak or tired Chills or shivering Felt cold Felt hot Sweating	11 items within Body/Systemic domain	items must be present to calculate domain score
Total	All above 32 items	Arithmetic mean of all 32 items within RSV-PRO	In the presence of missing data, the above conditions for the calculation of all domain scores must be met in order to calculate the RSV-PRO total score.

Table 3. Calculations and Conversion Formulae

Measurement	Formula
Time to alleviation from RSV-like symptoms	
Alleviation or “recovery” from RSV-like symptoms in adults with acute, laboratory confirmed RSV is defined as the first day a subject reports a RSV-PRO total score ≤ 1.0 AND all domain scores are ≤ 1.0.
 
Subjects with an abnormal value at the last assessment will be censored at the date and time of the last assessment

Time to alleviation from systemic and respiratory symptoms	
Alleviation or “recovery” from systemic and respiratory symptoms is defined as the first day a subject reports ‘not at all’ or ‘a little bit’ as severity for all items in the body/systemic and respiratory domain.
 
Subjects with an at least moderate score at the last assessment for these 2 domains will be censored at the date and time of the last assessment

4.2.5.1.2. Analysis Methods

Actual values and changes from baseline will be summarized by treatment group at each scheduled time point for the RSV-PRO domain and total scores. Mean \pm SE graphs over time for the actual values and changes from reference will be presented.

Time-to-alleviation will be analyzed in an exploratory sense using a summary table including number of subjects included in the analysis, number of subjects censored, 25th and 75th percentiles and median time to event, with 95% confidence intervals based on log-log transformation method, will be presented. The data will be presented graphically using the Kaplan-Meier estimate of the survival function. For each comparison of active versus placebo the stratified Gehan test will also be presented.

Frequency tabulation of each of the 32 items at the time point of return to return to usual activities and time point of return to usual health as defined in section 4.2.5.2.1.

4.2.5.2. Adult RSV Additional Questions

4.2.5.2.1. Definition

Table 4. Calculations and Conversion Formulae

Measurement	Formula
Time to return to usual activity	
The time in hours from the first dose of investigational product till the first one of 2 successive cases where the response is ‘Yes’ on RSV-PRO additional question 7 (“have you returned to your usual activities?”) . Time points with missing data are ignored in this analysis. The successive recordings cannot be within the same window. In case there are 2 recordings within a single window (i.e. morning window, afternoon window or evening window) the worst case within that window will be taken.
 
In cases where there are no sufficient recordings, the endpoint will be censored. Censoring will be at time of the last assessment if ticked as “Yes”; otherwise censoring will be the first window after the last assessment (lower limit). One exception is censoring at the Day 28 Visit (last study day for the subject). If the subject is not returned to usual activities/health on this day, the time of the last diary entry will be taken as the time of censoring.

Time to return to usual health	
The time in hours from the first dose of investigational product till the first one of 2 successive cases where the response is ‘Yes’ on RSV-PRO additional question 9 (“have you returned to your usual health?”). Time points with missing data are ignored in this analysis. The successive recordings cannot be within the same window. In case there are 2 recordings within a single window (i.e. morning window, afternoon window or evening window) the worst case within that window will be taken.
 
In cases where there are no sufficient recordings, the endpoint will be censored. Censoring will be at time of the last assessment if

	both items are ticked as “Yes”; otherwise censoring will be the first window after the last assessment (lower limit). One exception is censoring at the Day 28 Visit (last study day for the subject). If the subject is not returned to usual activities/health on this day, the time of the last diary entry will be taken as the time of censoring.
Time to full recovery	The maximum of the time to return to usual activity and usual health when both have an event, or the minimum of censored time(s) if at least one is censored.

4.2.5.2.2. Analysis Methods

Time to return to usual activity and usual health

Kaplan-Meier curves will be provided by treatment group. For each comparison of an active group versus placebo the stratified Gehan test will also be presented.

Other RSV additional questions

The number and percentage of subjects per category will be tabulated over time by treatment group for items 1 to 6 and item 8 of the RSV additional questions.

4.2.5.3. EQ-5D

4.2.5.3.1. Definitions

The EQ-5D questionnaire will be analyzed in 3 ways:

- 1) EQ-5D descriptive system: 5 dimensions (mobility, self-care, usual activities, pain/discomfort, anxiety/depression) with 5 possible levels (no (level code = 1), slight (level code = 2), moderate (level code=3), severe (level code=4), unable to/extreme (level code = 5)).

Dimension	Level	Interpretation	
1 Mobility	1	No problems	I have no problems in walking about
	2	Slight problems	I have slight problems walking
	3	Moderate problems	I have moderate problems walking
	4	Severe problems	I have severe problems walking
	5	Unable to	I am unable to walk
2 Self-care	1	No problems	I have no problems washing or dressing myself
	2	Slight problems	I have slight problems washing or dressing myself
	3	Moderate problems	I have moderate problems washing or dressing myself
	4	Severe problems	I have severe problems washing or dressing myself
	5	Unable to	I am unable to wash or dress myself
3 Usual activities	1	No problems	I have no problems doing my usual activities

		2	Slight problems	I have slight problems doing my usual activities
		3	Moderate problems	I have moderate problems doing my usual activities
		4	Severe problems	I have severe problems doing my usual activities
		5	Unable to	I am unable to do my usual activities
4	Pain/discomfort	1	No pain	I have no pain or discomfort
		2	Slight pain	I have slight pain or discomfort
		3	Moderate pain	I have moderate pain or discomfort
		4	Severe pain	I have severe pain or discomfort
		5	Extreme pain	I have extreme pain or discomfort
5	Anxiety/depression	1	Not anxious	I am not anxious or depressed
		2	Slightly anxious	I am slightly anxious or depressed
		3	Moderate anxious	I am moderately anxious or depressed
		4	Severe anxious	I am severely anxious or depressed
		5	Extreme anxious	I am extremely anxious or depressed

- 2) EQ-5D VAS: a continuous score ranging from 0 to 100.
- 3) EQ-5D Valuation index: The information of the 5 dimensions of the descriptive system summarized into one index.
 - a. Assign the level code 1, 2, 3, 4 and 5 to each level of the 5 dimensions (see table)
 - b. Create a health state for each patient-time point combination. A health state is a combination of 5 level codes; one level code for each dimension. The dimensions are ordered as described in the table above. E.g. health state 12311 indicates ‘no problems in walking about, slight problems washing or dressing myself, moderate problems to perform my usual activities, no pain or discomfort, not anxious or depressed’.
 - c. Assign an index value to each health state as defined on the EUROQol website (<http://www.euroqol.org/about-eq-5d/valuation-of-eq-5d/eq-5d-5l-value-sets.html>). EQ-5D health state is converted to a single summary index by applying a formula that essentially attaches weights to each of the levels in each dimension. The algorithm is based on the valuation of EQ-5D health states using the UK TTO (=time trade-off method) based value set. Based on the origin of the subjects, another method can be used.

4.2.5.3.2. Analysis Methods

Actual values and changes from baseline will be summarized by treatment group at each scheduled time point for the EQ-5D VAS and valuation index. Mean \pm SE graphs over time for the actual values and changes from reference will be generated.

The number and percentage of subjects per problem level will be tabulated over time by treatment group for each of the 5 dimensions.

This will be done for all subjects and in addition for the following subgroup: ≥ 50 to < 65 years and ≥ 65 years.

4.2.5.4. Katz-ADL

4.2.5.5. Definition

Katz-ADL is a status descriptor. A status change will be considered RSV-related if the subject evolved from independence before the RSV infection to dependence during or after RSV infection for each of the 6 different activities.

Measurement	Formula
Normalized Katz-Score	The normalized Katz score is the ratio of the actual Katz-score over the Katz-score pre-onset of RSV symptoms

4.2.5.5.1. Analysis

For each day the average Katz score will be presented by treatment group, as well as the change from baseline using both raw scores as normalized scores. Data will be presented using a mean (SE) plot over time, by treatment group.

The evolution of activities of Daily Living (ADL) as assessed by the Katz ADL will be analyzed by analyzing the time to return to pre-RSV functional status (Katz ADL score) as described in section [4.2.4.2](#).

Additionally, a cross-tabulation of the status changes versus the status before the RSV infection will be presented for each of the 6 different activities, over time and at the time of hospital discharge. This table will show the number and percentage of subjects with dependence and the number and percentage of subjects with an RSV-related status change.

The relationship between RSV RNA viral load and Katz ADL

The relationship between the RSV RNA (as measured by the PCR method) will be assessed using spearman rank correlation between the viral load and the Katz ADL normalized score for each combination of Days. This matrix of correlations will provide information if within each day the viral load is predictive of Katz functional status, but will also allow if there is a delayed relationship, meaning that viral load is predictive of future Katz functional statuses. A second approach will be to correlate the time to virus negativity with the Katz ADL baseline score marking censored cases. Other methods may be considered as appropriate.

The relationship between the Katz ADL and the subject eCOA responses.

The relationship between the Katz ADL and the scores of eCOA will be assessed using various measures. Katz baseline scores will be correlated with the time to alleviation from systemic and

respiratory symptoms as defined by the RSV-PRO. Subjects who are censored will be assumed to have alleviation of symptoms 1 day after censoring in this analysis. For the multidimensional aspects of the various patient reported measurements and the Katz scores and viral load a separate analysis plan will be issued.

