A secondary endpoint of high interest is the length of hospital stay. The length of hospital stay is in hours and taken from the start of treatment initiation to discharge and to readiness for discharge. The differences of active dose regimens versus placebo treatment will be estimated using the accelerated failure time model using appropriate contrasts; baseline covariates such as stratification factors, absence/presence of other viral or bacterial pathogens, RSV baseline log₁₀ viral load, and time from onset of first symptoms to treatment will be added when of predictive value based on blinded data. Treatment effects versus placebo will be reported as acceleration factors including 95% confidence intervals. Subjects for which no time point could be established (eg, withdrawal of informed consent before reaching the endpoint) will be (right-)censored at the latest time point at which it could be established that the endpoint was not reached. Subjects for whom discharge cannot be considered as a marker of adequate recovery (eg, subjects who die during hospitalization or who are transferred to a care facility with the same level of care as during hospitalization) will be censored at the planned final follow-up visit. No adjustments for multiplicity will be made. Analytical details will be provided in the SAP.

While this clinical endpoint is considered of high interest, the current sample size is determined by considerations on antiviral activity; for length of hospital stay the anticipation is that there will be too much heterogeneity to expect statistically significant separation of active groups versus placebo with the current sample size, even if a numerical trend is anticipated.

The impact of the baseline viral genotype and subtype on the antiviral activity will be explored.

Analysis of the viral sequencing results will be described in the SAP.

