1.2. Trial Design

This is a randomized, double-blind, placebo-controlled, parallel-grouped, multicenter, dose-finding study of ALS-008176.

A target of approximately 90 subjects, ≥ 50 years of age who are hospitalized with RSV, will be randomly assigned in this study with 30 subjects planned per treatment regimen.

Subjects will be randomized in a 1:1:1 ratio to Regimen A, B, or C:

- Regimen A (placebo): a single LD (Dose 1) followed by 9 MDs (Doses 2 to 10) of matching placebo, administered twice daily.

- Regimen B (low-dose ALS-008176): a single 750 mg LD (Dose 1) followed by nine 250 mg MDs (Doses 2 to 10) of ALS-008176, administered twice daily.
- Regimen C (high-dose ALS-008176): a single 1,000 mg LD (Dose 1) followed by nine 500 mg MDs (Doses 2 to 10) of ALS-008176, administered twice daily.

The randomization will be balanced by using randomly permuted blocks and will be stratified by region (Japan versus non-Japan) and age (≥ 50 to < 65 years and ≥ 65 years).

The study will be conducted in 3 phases: a screening phase, a treatment phase from Day 1 to Day 5/6 (depending on the timing of the LD), and a follow-up phase for a total of 28 days post randomization. In the follow-up phase, subjects will have assessments completed at Day 7, Day 10, Day 14, and Day 28. Depending on discharge date, assessments will be completed either while hospitalized or during outpatient visits. For hospitalized subjects additional assessments are done as per the Time and Events Schedule. The duration of the subject's participation will be approximately 28 days, screening period not included.

Screening for eligible subjects will be performed as soon as possible following admission to the emergency room or hospitalization, such that subjects are randomized within 5 days of RSV symptom onset. Men or women ≥ 50 years of age diagnosed with RSV infection based on a polymerase chain reaction (PCR)-based diagnostic assay (with or without co-infection with another respiratory pathogen) who have been (or will be) admitted to the hospital and who have signed informed consent will be enrolled.

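### Scoring censored subjects as recovered one day after censoring pulls the correlation between baseline Katz score and time to symptom alleviation towards zero

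*SAP*

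**What the plan says.** Among its measures of how the Katz score relates to patient-reported outcomes, SAP section 4.2.5.5.1 says "Katz baseline scores will be correlated with the time to alleviation from systemic and" respiratory symptoms. It does not name the coefficient. The next sentence gives the rule: "Subjects who are censored will be assumed to have alleviation of symptoms 1 day after censoring in this analysis".

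Who is censored is set out in SAP section 4.2.5.1.1, Table 3. The event is "defined as the first day a subject reports" only the two lowest severity levels on every item of the two domains. "Subjects with an at least moderate score at the last assessment for these 2 domains will be censored" at the date and time of that last assessment. The table has no separate rule for death or early withdrawal. Follow-up is "a follow-up phase for a total of 28 days post randomization" (SAP section 1.2).

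Elsewhere the SAP keeps censoring as censoring. For time to alleviation, section 4.2.5.1.2 states: "The data will be presented graphically using the Kaplan-Meier estimate of the survival function", with a stratified Gehan test for each active arm against placebo. For the companion viral analysis, section 4.2.5.5.1 states: "A second approach will be to correlate the time to virus negativity with the Katz ADL baseline score marking censored cases". No sensitivity analysis of the one-day rule is given.

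**The concern.** A censoring time is a lower bound on the recovery time. The rule turns that bound into an observed recovery one day later. For a subject who leaves early and unwell, a time that is probably long is replaced by one of the shortest in the data set.

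If more independent subjects recover sooner, the true correlation is negative. Placing still-symptomatic subjects among the early recoverers blurs it. If the subjects who leave early are mainly those with low Katz scores, short times are assigned to the very group expected to have long ones, and the loss is larger.

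The relationship between Katz score and the patient-reported responses is a stated exploratory objective, and this correlation is one of the measures that address it. What is at stake is whether that relationship is described accurately. No treatment claim depends on it.

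**Working it through.** **1. What the rule does to one subject.** Assigned time = censoring day + 1.
- Last seen symptomatic on Day 3: 3 + 1 = Day 4, treated as observed.
- Still symptomatic on Day 28: 28 + 1 = Day 29. Every observed event falls on or before Day 28, so this subject ranks last, which is correct for a rank correlation.
- Alleviated on Day 6 and then stops reporting: already an event, because the first qualifying day counts. The rule does not apply.

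Only loss or death before Day 28 while still symptomatic causes the problem.

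**2. Is there a plan figure to reproduce?** No. Neither document gives an expected correlation, a censoring rate or power for this analysis. The size below comes from simulation under assumed inputs.

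**3. Weak association.** From the SAP: 90 subjects and 28 days of follow-up. Assumed: a mean Spearman correlation near -0.18 with full follow-up, and the dropout patterns shown.

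| Assumed early dropout | Mean correlation under the rule | Share lost |
|---|---|---|
| None (censoring at Day 28 only) | -0.18 | 0 |
| 5-10%, unrelated to Katz | about -0.17 | (0.18 - 0.17)/0.18 = 6% |
| 5% (Katz 6) rising to 20% (Katz 0) | about -0.14 | (0.18 - 0.14)/0.18 = 22% |
| 15% (Katz 6) rising to 45% (Katz 0) | about -0.10 | (0.18 - 0.10)/0.18 = 44% |

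The last row also depends on the assumed Katz distribution. With Katz scores skewed towards 6, the same dropout pattern over Days 1-10 took a mean of -0.20 to -0.08.

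**4. Stronger associations, over a range of dropout.** Assumed: log-normal alleviation time with median 8 days and log-SD 0.7, and dropout on Days 1-14. The latent correlation is -0.5 in the first three rows, where full follow-up gives a mean Spearman correlation of -0.46.

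| Who drops out | 5% | 10% | 20% | 30% |
|---|---|---|---|---|
| Unrelated to Katz | -0.45 | -0.44 | -0.41 | -0.39 |
| Frailer subjects more often | -0.41 | -0.37 | -0.29 | -0.23 |
| Slower recoverers more often | -0.43 | -0.40 | -0.35 | -0.31 |
| Frailer, full-follow-up value -0.27 | -0.23 | -0.19 | -0.13 | -0.08 |

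Across these scenarios, 60-74% of early-censored subjects were scored at or below the median recovery time. Their times were understated by about 7-12 days on average.

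**5. Does keeping the censoring help?** In the -0.46 setting, a Cox model with full follow-up gives a hazard ratio of alleviation of 1.40 per Katz point. With frailty-related dropout of 5 / 10 / 20 / 30%:
- one-day rule, every time treated as an event: 1.33 / 1.29 / 1.21 / 1.16
- same subjects kept censored: 1.40 / 1.42 / 1.43 / 1.45

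Placing early dropouts last, at Day 29, is not a neutral substitute. With frailty-related dropout it overshoots the -0.46, giving -0.48 at 10% and -0.52 at 30%.

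**The case against.** The strongest reply is that the effect may be slight. The protocol works hard to keep diaries going: relatives or trained staff may enter answers, the site can interview the subject by phone every day after discharge, and a gap of more than 36 hours triggers contact (Protocol sections 9.1.1 and 17.6). Stopping study drug does not end follow-up (section 10.2). With 5-10% dropout unrelated to Katz the shift is about 0.01. At 90 subjects the standard error of a correlation is about 1/√(90 - 3) = 0.11, so even a shift of 0.07 is under one standard error. The analysis is exploratory, carries no alpha and is one of several measures. The SAP also promises a separate plan for the multidimensional relationships among these scores.

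Most of this stands, and it is why the point ranks low. It does not justify the rule. Proxy entry and telephone calls cannot recover data after death or withdrawal of consent, and the protocol's rationale (section 1.2) cites 60-day mortality of up to 13.8% in hospitalised adults. A shift smaller than the sampling error is still systematic, and it can be avoided.

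A reader might also infer that frail patients will in fact stop reporting more often. The documents do not say so. It is an assumption, and the measures above work against it. Some attenuation remains without it.

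**Conclusion.** Wrong as written, with low consequence. The rule biases the correlation towards zero through subjects lost, withdrawn or dead early while symptomatic. With 90 subjects and a correlation near -0.18, the estimate becomes about -0.17 if 5-10% drop out regardless of Katz, and about -0.14 to -0.10 if frailer subjects leave early. These sizes rest on assumed dropout, an assumed Katz distribution and an assumed negative association, none of which the documents supply.

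A reader might go further and conclude that the rule could reverse the association. The documents do not support that. The mean correlation stayed negative in every scenario run. A single trial can show the wrong sign when the association is weak: in the skewed-Katz scenario with 15-45% dropout, the share of samples at zero or above rose from 2% to 22%. That combines attenuation with sampling error. A reversal on average would need a weaker association, or dropout tied more tightly to frailty, than any case examined, and nothing in the documents points to either.

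**What to change.** In SAP section 4.2.5.5.1, delete the one-day rule and treat these times as right-censored, in line with section 4.2.5.1.2. Fit an accelerated failure time model, using the framework in section 4.2.4.2, or a Cox model, for time to alleviation with baseline Katz score as covariate. Report the effect with a 95% confidence interval. If a correlation is also shown, name the coefficient and mark the censored cases, as the viral analysis does.

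Two statements should accompany the model:
- **Deaths.** Say how they are handled. The documents give no settled convention: for length of stay, Protocol section 11.3 says that subjects whose discharge does not mark recovery, deaths included, "will be censored at the planned final follow-up visit", while SAP Table 1 censors at the time of death.
- **Assumption.** Say that the model takes censoring as non-informative given Katz score.

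The cost is one added model specification and minor programming. It should not be assumed that the model already exists: section 4.2.4.2 applies the accelerated failure time model only to endpoints for which it is specified, compares active arms with placebo, and does not list Katz among its covariates. The SAP specifies no Cox model. Data collection, sample size, the primary endpoint and its alpha are unaffected.
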